## 5.2 Trial Treatments

The treatment to be used in this trial is outlined below in Table 2

Table 2 Trial Treatment

Drug	Dose/Potency	Dose Frequency	Route of Administration	Regimen/Treatment Period	Use
Pembrolizumab	200 mg IV	Q3W	IV infusion	Day 1 of each 3 week cycle	Experimental
sEphB4-HSA	10 mg/kg	Q1W	IV infusion	Day 1, 8,15 of each 3 week cycle	Experimental

Trial treatment should begin on the day of randomization or as close as possible to the date on which treatment is allocated/assigned. Trial therapy will continue up to 24 months, until disease progression, unacceptable toxicity, withdrawal of consent, investigator discretion, or sponsor decision to terminate the trial. Patients who stop therapy after 24 months and experience subsequent disease progression, may resume therapy for another 24 months.

## 5.2.1 Dose Selection/Modification

### 5.2.1.1 Dose Selection

The rationale for selection of doses to be used in this trial is provided in Section 4.0 – Background and Rationale.

Details on preparation and administration of pembrolizumab (MK-3475) are provided in the Pharmacy Manual.

### 5.2.1.2 Dose Modification for Pembrolizumab

Adverse events (both non-serious and serious) associated with pembrolizumab exposure may represent an immunologic etiology. These adverse events may occur shortly after the first dose or several months after the last dose of treatment. Pembrolizumab must be withheld for drug-related toxicities and severe or life-threatening AEs as per 3 below. See Section 5.6 for supportive care guidelines, including use of corticosteroids.

Table 3 Dose Modification Guidelines for Drug-Related Adverse Events

Toxicity	Hold Treatment For Grade	Timing for Restarting Treatment	Treatment Discontinuation
Diarrhea/Colitis	2-3	Toxicity resolves to Grade 0-1	Toxicity does not resolve within 12 weeks of last dose or inability to reduce corticosteroid to 10 mg or less of prednisone or equivalent per day within 12 weeks
	4	Permanently discontinue	Permanently discontinue
AST, ALT, or Increased Bilirubin	2	Toxicity resolves to Grade 0-1	Toxicity does not resolve within 12 weeks of last dose
	3-4	Permanently discontinue (see exception below) a	Permanently discontinue
Type 1 diabetes mellitus (if new onset) or Hyperglycemia	T1DM or 3-4	Hold pembrolizumab for new onset Type 1 diabetes mellitus or Grade 3-4 hyperglycemia associated with evidence of beta cell failure	Resume pembrolizumab when patients are clinically and metabolically stable
Hypophysitis	2-4	Toxicity resolves to Grade 0-1. Therapy with pembrolizumab can be continued while endocrine replacement therapy is instituted	Toxicity does not resolve within 12 weeks of last dose or inability to reduce corticosteroid to 10 mg or less of prednisone or equivalent per day within 12 weeks
Hyperthyroidism	3	Toxicity resolves to Grade 0-1	Toxicity does not resolve within 12 weeks of last dose or inability to reduce corticosteroid to 10 mg or less of prednisone or equivalent per day within 12 weeks
	4	Permanently discontinue	Permanently discontinue
Hypothyroidism		Therapy with pembrolizumab can be continued while thyroid replacement therapy is instituted	Therapy with pembrolizumab can be continued while thyroid replacement therapy is instituted
Infusion Reaction	2 b	Toxicity resolves to Grade 0-1	Permanently discontinue if toxicity develops despite adequate premedication
	3-4	Permanently discontinue	Permanently discontinue
Pneumonitis	2	Toxicity resolves to Grade 0-1	Toxicity does not resolve within 12 weeks of last dose or inability to reduce corticosteroid to 10 mg or less of prednisone or equivalent per day within 12 weeks
	3-4	Permanently discontinue	Permanently discontinue

Toxicity	Hold Treatment For Grade	Timing for Restarting Treatment	Treatment Discontinuation
Renal Failure or Nephritis	2	Toxicity resolves to Grade 0-1	Toxicity does not resolve within 12 weeks of last dose or inability to reduce corticosteroid to 10 mg or less of prednisone or equivalent per day within 12 weeks
	3-4	Permanently discontinue	Permanently discontinue
All Other Drug-Related Toxicity a	3 or Severe	Toxicity resolves to Grade 0-1	Toxicity does not resolve within 12 weeks of last dose or inability to reduce corticosteroid to 10 mg or less of prednisone or equivalent per day within 12 weeks
	4	Permanently discontinue	Permanently discontinue

**Note: Permanently discontinue for any severe or Grade 3 drug-related AE that recurs or any life-threatening event.**

a For patients with liver metastasis who begin treatment with Grade 2 AST or ALT, if AST or ALT increases by greater than or equal to 50% relative to baseline and lasts for at least 1 week then patients should be discontinued.

b If symptoms resolve within one hour of stopping drug infusion, the infusion may be restarted at 50% of the original infusion rate (e.g., from 100 mL/hr to 50 mL/hr). Otherwise dosing will be held until symptoms resolve and the subject should be premedicated for the next scheduled dose; Refer to Table 2 – Infusion Treatment Guidelines for further management details.

c Patients with intolerable or persistent Grade 2 drug-related AE may hold study medication at physician discretion. Permanently discontinue study drug for persistent Grade 2 adverse reactions for which treatment with study drug has been held, that do not recover to Grade 0-1 within 12 weeks of the last dose.

Dosing interruptions are permitted in the case of medical / surgical events or logistical reasons not related to study therapy (e.g., elective surgery, unrelated medical events, patient vacation, and/or holidays). Subjects should be placed back on study therapy within 3 weeks of the scheduled interruption, unless otherwise discussed with the Sponsor. The reason for interruption should be documented in the patient's study record. Patients who permanently discontinue pembrolizumab may continue treatment with single agent sEphB4-HSA at the discretion of the treating physician.

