## 5.4 Rescue Medications & Supportive Care

### 5.4.1 Supportive Care Guidelines

Subjects should receive appropriate supportive care measures as deemed necessary by the treating investigator. Suggested supportive care measures for the management of adverse events with potential immunologic etiology are outlined below. Where appropriate, these guidelines include the use of oral or intravenous treatment with corticosteroids as well as additional anti-inflammatory agents if symptoms do not improve with administration of corticosteroids. Note that several courses of steroid tapering may be necessary as symptoms may worsen when the steroid dose is decreased. For each disorder, attempts should be made to rule out other causes such as metastatic disease or bacterial or viral infection, which might require additional supportive care. The treatment guidelines are intended to be applied when the investigator determines the events to be related to pembrolizumab.

Note: if after the evaluation the event is determined not to be related, the investigator does not need to follow the treatment guidance (as outlined below). Refer to Section 5.2.1 for dose modification.

It may be necessary to perform conditional procedures such as bronchoscopy, endoscopy, or skin photography as part of evaluation of the event.

- **Pneumonitis:**

- For **Grade 2 events**, treat with systemic corticosteroids. When symptoms improve to Grade 1 or less, steroid taper should be started and continued over no less than 4 weeks.
- For **Grade 3-4 events**, immediately treat with intravenous steroids. Administer additional anti-inflammatory measures, as needed.
- Add prophylactic antibiotics for opportunistic infections in the case of prolonged steroid administration.
- If there is recurrence of grade 2 pneumonitis, pembrolizumab will be permanently discontinued.

- **Diarrhea/Colitis:**

Subjects should be carefully monitored for signs and symptoms of enterocolitis (such as diarrhea, abdominal pain, blood or mucus in stool, with or without fever) and of bowel perforation (such as peritoneal signs and ileus).

- All subjects who experience diarrhea/colitis should be advised to drink liberal quantities of clear fluids. If sufficient oral fluid intake is not feasible, fluid and electrolytes should be substituted via IV infusion. For Grade 2 or higher diarrhea, consider GI consultation and endoscopy to confirm or rule out colitis.

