- For **Grade 2 diarrhea/colitis**, administer oral corticosteroids.
- For **Grade 3 or 4 diarrhea/colitis**, treat with intravenous steroids followed by high dose oral steroids.
- When symptoms improve to Grade 1 or less, steroid taper should be started and continued over no less than 4 weeks.
- **Type 1 diabetes mellitus (if new onset, including diabetic ketoacidosis [DKA]) or ≥ Grade 3 Hyperglycemia, if associated with ketosis (ketonuria) or metabolic acidosis (DKA)**
  - For **T1DM or Grade 3-4 Hyperglycemia**
    - Insulin replacement therapy is recommended for Type I diabetes mellitus and for Grade 3-4 hyperglycemia associated with metabolic acidosis or ketonuria.
    - Evaluate patients with serum glucose and a metabolic panel, urine ketones, glycosylated hemoglobin, and C-peptide.
- **Hypophysitis:**
  - For **Grade 2** events, treat with corticosteroids. When symptoms improve to Grade 1 or less, steroid taper should be started and continued over no less than 4 weeks. Replacement of appropriate hormones may be required as the steroid dose is tapered.
  - For **Grade 3-4** events, treat with an initial dose of IV corticosteroids followed by oral corticosteroids. When symptoms improve to Grade 1 or less, steroid taper should be started and continued over no less than 4 weeks. Replacement of appropriate hormones may be required as the steroid dose is tapered.
- **Hyperthyroidism or Hypothyroidism:**

Thyroid disorders can occur at any time during treatment. Monitor patients for changes in thyroid function (at the start of treatment, periodically during treatment, and as indicated based on clinical evaluation) and for clinical signs and symptoms of thyroid disorders.

  - **Grade 2** hyperthyroidism events (and **Grade 2-4** hypothyroidism):
    - In hyperthyroidism, non-selective beta-blockers (e.g. propranolol) are suggested as initial therapy.
    - In hypothyroidism, thyroid hormone replacement therapy, with levothyroxine or liothyroinine, is indicated per standard of care.
  - **Grade 3-4** hyperthyroidism

- Treat with an initial dose of IV corticosteroid followed by oral corticosteroids. When symptoms improve to Grade 1 or less, steroid taper should be started and continued over no less than 4 weeks. Replacement of appropriate hormones may be required as the steroid dose is tapered.
- **Hepatic:**
  - For **Grade 2** events, monitor liver function tests more frequently until returned to baseline values (consider weekly).

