### **7.2.4 Evaluating Adverse Events**

An investigator who is a qualified physician will evaluate all adverse events according to the NCI Common Terminology for Adverse Events (CTCAE), version 4.0. Any adverse event which changes CTCAE grade over the course of a given episode will have each change of grade recorded on the adverse event case report forms/worksheets.

All adverse events regardless of CTCAE grade must also be evaluated for seriousness.

Table 6 Evaluating Adverse Events

An investigator who is a qualified physician, will evaluate all adverse events as to:

V4.0 CTCAE Grading	Grade 1	Mild; asymptomatic or mild symptoms; clinical or diagnostic observations only; intervention not indicated.
	Grade 2	Moderate; minimal, local or noninvasive intervention indicated; limiting age-appropriate instrumental ADL.
	Grade 3	Severe or medically significant but not immediately life-threatening; hospitalization or prolongation of hospitalization indicated; disabling; limiting self-care ADL.
	Grade 4	Life threatening consequences; urgent intervention indicated.
	Grade 5	Death related to AE
Seriousness	A serious adverse event is any adverse event occurring at any dose or during any use of Merck product that:	
	† Results in death; or	
	† Is life threatening; or places the subject, in the view of the investigator, at immediate risk of death from the event as it occurred (Note: This does not include an adverse event that, had it occurred in a more severe form, might have caused death.); or	
	† Results in a persistent or significant disability/incapacity (substantial disruption of one's ability to conduct normal life functions); or	
	† Results in or prolongs an existing inpatient hospitalization (hospitalization is defined as an inpatient admission, regardless of length of stay, even if the hospitalization is a precautionary measure for continued observation. (Note: Hospitalization for an elective procedure to treat a pre-existing condition that has not worsened is not a serious adverse event. A pre-existing condition is a clinical condition that is diagnosed prior to the use of a Merck product and is documented in the patient's medical history.); or	
	† Is a congenital anomaly/birth defect (in offspring of subject taking the product regardless of time to diagnosis); or	

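### Table 3 lets pembrolizumab resume after Grade 4 hypophysitis or Grade 4 hyperglycemia against its own note on life-threatening events, and omits Section 5.4.1's rule on recurrent Grade 2 pneumonitis

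*Combined protocol and SAP*

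**What the plan says.** Table 3 in Section 5.2.1.2 sets out, by toxicity and grade, when pembrolizumab is held, restarted or stopped.

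- **Hypophysitis, Grades 2 to 4 in one row.** Restart once the event is down to Grade 0 or 1; the row adds "Therapy with pembrolizumab can be continued while endocrine replacement therapy is instituted". The discontinuation column applies if "Toxicity does not resolve within 12 weeks of last dose or inability to reduce corticosteroid to 10 mg or less of prednisone" (or equivalent), with a 12-week limit on the steroid reduction as well.
- **Type 1 diabetes or hyperglycemia.** "Hold pembrolizumab for new onset Type 1 diabetes mellitus or Grade 3-4 hyperglycemia associated with evidence of beta cell failure". The entry in the discontinuation column is "Resume pembrolizumab when patients are clinically and metabolically stable".
- **Pneumonitis, Grade 2.** Hold, then restart at Grade 0 or 1, with the same discontinuation triggers as hypophysitis. Recurrence is not mentioned.

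The bold note below the table says "Permanently discontinue for any severe or Grade 3 drug-related AE that recurs or any life-threatening event". Table 6 in Section 7.2.4 describes Grade 4 as "Life threatening consequences; urgent intervention indicated".

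Section 5.4.1 (Supportive Care Guidelines) adds for pneumonitis: "If there is recurrence of grade 2 pneumonitis, pembrolizumab will be permanently discontinued". For diabetes and hyperglycemia it says "Insulin replacement therapy is recommended for Type I diabetes mellitus and for Grade 3-4 hyperglycemia associated with metabolic acidosis or ketonuria", and gives no discontinuation rule there or under hypophysitis.

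The opening paragraph of Section 5.2.1.2 sends the reader to Section 5.6 for supportive care. Section 5.6 is the withdrawal section; supportive care is Section 5.4.

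**The concern.** A dose-modification table is what a site consults when a patient has a serious immune event, so each grade should lead to one action. Here the row and the note can lead to different actions for the same Grade 4 endocrine event, and the rule on recurrent pneumonitis is absent from the table where a site would look for it. Whether a patient is given pembrolizumab again could then depend on which sentence the site reads. That is a safety matter for the patient and a source of uneven handling between sites.

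**Working it through.** No arithmetic applies beyond a count of rows. The check sets the passages side by side, case by case.

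**How the table treats Grade 4 elsewhere.** Table 3 has ten toxicity rows, and nine name Grade 4. Seven of the nine stop pembrolizumab permanently at that grade: diarrhea/colitis, liver tests, hyperthyroidism, infusion reaction, pneumonitis, renal events, and all other drug-related toxicity. The liver row also flags an exception by footnote. The remaining two (9 − 7 = 2) are hypophysitis and diabetes/hyperglycemia; they include Grade 4 in a hold-and-resume instruction and carry no footnote tying them to the note or exempting them from it. The tenth row, hypothyroidism, names no grade and is left out of the count.

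**Case by case.**

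1. *Grade 4 hypophysitis.* The row allows restart on resolution, or continuation while hormones are replaced. The note, read with the Grade 4 definition, requires a permanent stop. The two conflict.
2. *Grade 4 hyperglycemia with beta cell failure.* The row allows resumption once the patient is stable. The note, read the same way, requires a permanent stop. The two conflict.
3. *Recurrent Grade 2 pneumonitis.* Read alone, the Table 3 row allows another restart on resolution. The note's recurrence clause covers severe or Grade 3 events, so it does not reach Grade 2. Section 5.4.1 requires a permanent stop. The rule is missing from the table.
4. *A single Grade 2 pneumonitis that resolves in time.* Table 3 allows restart, and neither the note nor Section 5.4.1 requires a stop. There is no conflict.

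**Whether a site would find the rule in case 3.** The pointer in Section 5.2.1.2 goes to Section 5.6. For unacceptable adverse experiences, Section 5.6 points back to Section 5.2.1.2. A reader following those references from the dose table goes round without reaching Section 5.4.1. Section 5.4.1 does refer the reader to Section 5.2.1, but that helps only someone already there. It also introduces its measures as suggestions, which leaves the force of the recurrence rule unclear.

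**The case against.** Three arguments on the other side have weight.

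*The note need not catch every Grade 4 event.* Table 6 has a separate seriousness criterion for life-threatening events: immediate risk of death, in the investigator's view, from the event as it occurred. If the note means that, a Grade 4 laboratory or hormonal event that falls short of it stays with its row. This narrows the conflict but does not remove it: an event that meets the criterion still has a row saying resume and a note saying stop. The protocol does not say which meaning the note uses.

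*Specific rows may be deliberate exceptions to a general note.* That is a reasonable reading, since these rows name Grade 4 and the other Grade 4 rows stop the drug. The opposite reading, that the note overrides every row, is also reasonable. The documents state neither.

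*Table 3 and Section 5.4.1 can both be followed for pneumonitis.* A site can restart after one episode and stop on recurrence. This stands: the pneumonitis point is an omission and a wrong cross-reference, not two opposed instructions.

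A reader might also infer that any resolved Grade 2 pneumonitis is in conflict, or that the note and Section 5.4.1 both demand a stop for the same patients. The text does not support this. Section 5.4.1 acts only on recurrence and has no stopping rule for hypophysitis or hyperglycemia, while the note does not reach Grade 2 pneumonitis. Nor does the hyperglycemia row make resumption depend on replacement therapy: its condition is stability, and insulin appears only in Section 5.4.1.

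**Conclusion.** The point holds as an internal inconsistency in a stated safety rule. It covers two Grade 4 endocrine situations in which row and note disagree, and one recurrence rule missing from the table. The endocrine part assumes that the note's life-threatening event includes CTCAE Grade 4 as Section 7.2.4 describes it, and that a note with no stated exception applies to every row. On the narrower seriousness reading, fewer patients are affected but the conflict remains.

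A reader might go further and infer that the safety results must shift, for example by 1/25 = 4 percentage points of the discontinuation rate (Section 4.2.3.1) per patient handled differently, or through the toxicity count in Section 8.2. The documents do not show this:

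- They give no frequency for any of the three events.
- The NSCLC cohort has been closed since the July 2018 interim analysis.
- Section 5.2.1.2 lets sEphB4-HSA continue after pembrolizumab is permanently stopped, so such a stop is not automatically discontinuation of therapy.
- The Section 8.2 monitoring rule concerns the first two courses, which leaves little time for a pneumonitis to resolve, be re-treated and recur.

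An effect on those measures is possible but not established. The case for change rests on patient safety and consistent conduct.

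**What to change.** Reconcile the Table 3 rows, the bold note and Section 5.4.1 so that each grade and each recurrence gives one instruction:

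- State whether the note applies to the hypophysitis and the diabetes/hyperglycemia rows, and what the note means by life-threatening: CTCAE Grade 4 or the seriousness criterion in Table 6. Say at the same time how the note relates to the hypothyroidism row, which names no grade.
- Make the rule on recurrent Grade 2 pneumonitis the same in the Table 3 row and in Section 5.4.1, and say whether it is binding or suggested.
- Correct the supportive-care reference in Section 5.2.1.2 from Section 5.6 to Section 5.4.

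The sponsor's medical lead decides which instruction stands; this review takes no position on that. The cost is protocol amendment wording and a letter to sites, with no extra patients or procedures.

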### 5.2.1.3 Dose Modification for sEphB4-HSA

sEphB4-HSA must be withheld for drug-related toxicities and severe or life-threatening AEs as per Table 3b below.

Dose modification scheme is as follows:

- (1) Dose level 0: 10 mg/Kg q week
- (2) Dose level -1: 5 mg/Kg q week
- (3) Dose level -2: 2.5 mg/Kg q week

Patients can have a maximum of 2 dose reductions for drug-related toxicity beyond which they will be removed from the study. If patient requires more than 2 dose reductions, they will be treated with single agent pembrolizumab or be removed from study treatment at the discretion of the treating physician.

#### Dose Modification Guidelines for sEphB4-HSA-Related Adverse Event

Toxicity	Hold Treatment For Grade	Timing for Restarting Treatment	Discontinue Subject
Unmanageable  non-hematologic toxicity other than alopecia	3-4	
Toxicity resolves to Grade 0-1 or baseline, one dose level reduction.
 
Patients with toxicities that are manageable with supportive therapy may not require dose reductions (for example, patients with Grade 3-4 nausea, vomiting or diarrhea must have persistent toxicity despite having received optimal supportive therapy in order to require a dose reduction). Patients with <math>\geq</math> Grade 3 electrolyte abnormalities, if easily managed medically (return to Grade 2 or less within 72 hours), do not require a dose reduction.
	Treatment can be continued with supportive management as described in 5.6.1
AST, ALT	2	
Subjects who experience a grade 2 AST and or ALT will have subsequent doing held until the AST/ALT return to grade 0/1 and then can resume the prior dose, however, if the return to grade 0/1 takes longer than 7 days, the subject will be treated at a 1 level dose reduction
 
Grade 3 AST and/or ALT that represents at least a two grade increase from baseline or <math>\text{AST/ALT} \geq 10 \times \text{ULN}</math> –hold therapy, recheck weekly, initiate retreatment when resolved to baseline with one dose level reduction.
	Toxicity does not resolve within 12 weeks of last dose.
	3-4	Permanently discontinue (see exception below) 	Permanently discontinue
Hypertension 	2	Initiate antihypertensive drugs	Treatment can continue while antihypertensive drugs are initiated

Toxicity	Hold Treatment For Grade	Timing for Restarting Treatment	Discontinue Subject
	3	First occurrence, if asymptomatic and on antihypertensive therapy, may continue treatment, and optimize antihypertensive therapy.  Second occurrence, despite antihypertensive therapy, hold until grade < 3, one dose level reduction	Treatment can continue while antihypertensive drugs are initiated
	4	Permanently discontinue sEphB4-HSA	Permanently discontinue sEphB4-HSA
Thrombocytopenia	3-4	Toxicity resolves to Grade 0-1, one dose level reduction	Toxicity does not resolve within 12 weeks of last dose.
Neutropenia	4	Toxicity resolves to Grade 0-1, one dose level reduction	Treatment can continue with GCSF support

